#### Healthy Volunteers

- Volunteers without history of brain cancer.
- 13 years old and above.
- No pregnant subjects will be enrolled.
- No contraindications to MR exam(s) – healthy volunteers will use the same screening process utilized for MDACC patients.
- Written Informed consent must be obtained by the patient (age 13-17)'s parent or legally authorized representative (LAR)

### 3.2 Exclusion Criteria

#### Patients

- Contraindication to MR imaging.
- Absolute or relative contra-indication to 3T MRI due to metallic foreign bodies and devices and/or other conditions that are not MR safe, which include implants with unknown behavior in 3T MRI as well as:
  - electronically, magnetically, and mechanically activated implants
  - ferromagnetic or electronically operated active devices like automatic cardioverter defibrillators and cardiac pacemakers
  - metallic splinters in the eye
  - ferromagnetic hemostatic clips in the central nervous system (CNS) or body
  - cochlear implants

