## 3 ELIGIBILITY

### 3.1 Inclusion Criteria

#### Patients

- 13 years old and above.
- Written Informed consent must be obtained by the patient (age 13-17)'s parent or legally authorized representative (LAR)
- Patients must meet one set of inclusion criteria:
  - Newly identified and untreated primary brain tumor or metastasis of at least 5 mm or greater in size.
    - Suspected central nervous system neoplasms will require agreement from a study neuroradiologist and a study neurosurgeon, neuro-oncologist, or a radiation oncology that a lesion exists that is most likely either a primary brain tumor or a metastasis.
    - Patients with suspected brain metastasis must also have a history of solid organ malignancy.
  - History of primary brain tumor or metastasis treated with surgery, radiation, chemotherapy, or immunotherapy with new or increasing signal on MR imaging that is suspicious for progressive disease (treatment failure).
    - Suspected recurrent neoplasms will require agreement from a study neuroradiologist and a study neurosurgeon, radiation oncologist, or neuro-oncologist that lesion behavior is suspicious for recurrent disease.

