## 3.3 NUMBER OF PARTICIPANTS

One hundred (100) patients will be studied. Up to twenty (20) healthy volunteers will be studied for the purposes of MRI sequence optimization.

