## 4.3 Houston Methodist Research Institute (HMRI) Registration

If inclusion/exclusion criteria are met and patients agree to participate in the study, the research study team will then contact the Houston Methodist Research Institute (HMRI) to register the patient and schedule their research MRI scan. Patient information including patient name, date of birth, prior allergic reaction to gadolinium based contrast agents, prior surgical history (as it pertains to surgical implants which may be a contraindication to MR scanning) which will be provided to HMRI as part of the study procedure (Appendix A – MRI Safety Questionnaire) and Referral Questionnaire for MDACC (Appendix B).

A copy of the completed MRI safety questionnaire and Referral Questionnaire for MDACC will be stored in REDCap and only authorized members of research team from MD Anderson (MDA) & HMRI who signed the delegation of authority log will have access to the data.

Research patients and volunteers will be contacted by MDA DI research study staff and given instruction for their research MRI scan once it is scheduled at HMRI.

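### The patient device exclusion, including its only clause on unknown implant behaviour, is written for 3T, but the only research scan is at 7.0T

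*Combined protocol and SAP*

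**What the plan says.** All references are to the combined protocol and SAP.

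- **Section 3.2 (patients), device exclusion.** It covers "Absolute or relative contra-indication to 3T MRI due to metallic foreign bodies" and devices, and includes "implants with unknown behavior in 3T MRI". A list of named items follows, among them "ferromagnetic hemostatic clips in the central nervous system (CNS) or body".
- **Section 3.2 (patients), general exclusion.** A separate first bullet reads "Contraindication to MR imaging". It gives no field strength and does not mention implants.
- **Section 3.1 (patients).** Patients with a tumour "treated with surgery, radiation, chemotherapy, or immunotherapy" are eligible when new or increasing signal is suspicious for progression.
- **Section 3.1 (volunteers).** It says that "healthy volunteers will use the same screening process utilized for MDACC patients".
- **Sections 4.4 and 4.6.** The study MRI is on a 7.0T system, with one research session per patient.
- **Section 4.1.** Among the study procedures, 3T appears only here. The 7T scan should fall within 30 days of an MRI done at 3T or 1.5T.
- **Section 4.3.** Once the criteria are met and the patient agrees, the 7T site receives surgical history as it bears on "surgical implants which may be a contraindication to MR scanning", with a safety questionnaire and a referral questionnaire.
- **Sections 3.3 and 7.3.** "One hundred (100) patients will be studied". About 90% are expected to have a tumour, half metastasis and half primary, with about half of each treated. The plan expects 20 to 25 patients in each of the four tumour groups.

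**The concern.** The exposure that this study adds is a 7T scan, so its device criterion should ask whether the patient's hardware is acceptable at 7T. It asks about 3T instead. The authors judged that unknown implant behaviour needed its own clause, but that clause refers to a scanner the study does not use.

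The gap falls on a population the study recruits. Previously operated patients may carry retained passive hardware. The named list excludes certain devices at any field strength, but for haemostatic clips it names only ferromagnetic ones. A non-ferromagnetic clip that is acceptable at 3T and uncharacterised at 7T passes the criterion as written.

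For such a patient, the decision then depends on how staff read the general bullet and on a later step at the 7T site whose acceptance rule is not stated in the available text.

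**Working it through.** **1. Is the criterion matched to the scan?**

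| Item | Section | Field strength |
|---|---|---|
| Device contraindication | 3.2 | 3T |
| Unknown-behaviour clause (the only one) | 3.2 | 3T |
| General MR exclusion | 3.2 | none named |
| Prior scan used for timing | 4.1 | 3T or 1.5T |
| Research scan, one session | 4.4, 4.6 | 7.0T |

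Across sections 3.1 and 3.2, 3T appears twice and 7T not at all. The prior scan in section 4.1 does not explain the 3T wording: it is not the research session, and it may be at 1.5T.

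**2. Does other text supply a 7T rule?**

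- The general bullet could be read to include 7T, but it does not address unknown behaviour.
- Section 4.3 sends implant history to the 7T site before the scan, but states no acceptance rule.
- The head SAR limit in section 4.4 says nothing about implants.
- Section 8 names contrast allergy as a risk and does not mention implants.
- Section 10 lists the questionnaires, but their content is not in the available text. A 7T rule there can be neither confirmed nor ruled out.

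**3. What could the fix cost in precision?**

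The documents give no rate of affected patients, so this is a range under assumptions. It measures the cost of the fix, not the number of patients at risk.

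The plan's own figure comes first. Section 7.3 takes a CEST CNR mean of 14.9, an SD of 3.0 and n = 20. The half-width is 1.96 × 3.0/√20 = 1.31, so the interval is 14.9 ± 1.31, or 13.6 to 16.2. This matches the plan.

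Expected treated tumour patients: 100 × 0.90 × 0.5 = 45, or 22.5 in each of the two treated groups.

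Suppose that a share p of otherwise eligible treated candidates cannot be cleared, that treated and untreated candidates arrive equally, and that 90 tumour patients are still enrolled. Then:

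- treated patients = 90(1 − p)/(2 − p)
- n per treated group = half of that
- half-width = 1.96 × 3.0/√n

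| p (assumed) | Treated patients | Per treated group | 95% CI half-width |
|---|---|---|---|
| 0 | 45.0 | 22.5 | 1.24 |
| 10% | 42.6 | 21.3 | 1.27 |
| 20% | 40.0 | 20.0 | 1.31 |
| 30% | 37.1 | 18.5 | 1.37 |
| 50% | 30.0 | 15.0 | 1.52 |

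The treated groups stay within the planned 20 to 25 up to p = 20%. The p = 0 row assumes that the 7T site turns nobody away now. If it already does, the added loss is smaller than shown.

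**The case against.** The strongest reply is that an unsafe scan does not follow from the wording.

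- The only MRI the protocol itself performs is at 7T, so a bullet excluding any contraindication to MR imaging naturally covers it.
- The 7T site receives implant history and a safety questionnaire before the scan. If that step works, the result is an enrolled patient who is not scanned.
- Any 7T rule most likely sits in the questionnaires, which are listed but not in the available text.
- No part of the documents says that a given implant is acceptable at 3T and unsafe or uncharacterised at 7T. The clip is an illustration.
- The named list is broad and even bars non-ferromagnetic stapedial implants.
- No endpoint or analysis is affected.

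Much of this stands. It would be wrong to say that the study has no 7T safety screening, and neither the number of patients affected nor the practical harm can be established. The interval widths above say nothing about risk. But none of these points makes 3T the right criterion for a 7T exposure. The mismatch is in the stated rule itself, so it is more than detail missing from the available text. The site step also comes after eligibility has been decided.

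**Conclusion.** The concern holds. Both field-strength references in the patient device exclusion name 3T, and the only research scan is at 7.0T. As written, the clause on unknown behaviour does not catch hardware that is known at 3T and unknown at 7T. Other safeguards may catch it, but none states a rule for that case in the available text.

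This should be fixed, with medium confidence. The wording mismatch is certain. Its practical consequence is not, because it depends on how the general bullet is applied, on the content of the questionnaires, and on how many patients carry such hardware. The cost figures rest on assumed values of p, equal arrival of treated and untreated candidates, and accrual continuing to 100.

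**What to change.** In section 3.2 (patients), replace 3T with 7T in both places and leave the named list unchanged. Then add a sentence that qualifies the unknown-behaviour clause: *Hardware not characterised at 7T is excluded unless the 7T site's MR safety review documents it as acceptable before the scan.* It should be drafted as an exception to that clause, so that the two do not read as an outright exclusion and a conditional one side by side. This formalises the step already in section 4.3 and does not bar every patient with uncharacterised hardware.

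Volunteers need no separate wording provided that the shared screening process in section 3.1 applies the amended rule. The team should confirm this.

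The cost is a short eligibility amendment and one documented clearance step at the 7T site. The downside is that an unknown number of patients with retained hardware, mainly in the treated groups, become ineligible or need clearance. Under the assumptions above, a treated group falls below 20 only if more than about 20% of treated candidates cannot be cleared.

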# Proprietary Information of MD Anderson

Protocol No: 2019-1032

Version No: 10

Version Date: August 25, 2023

- other pacemakers, e.g., for the carotid sinus
- insulin pumps and nerve stimulators
- non-MR safe lead wires
- prosthetic heart valves (if dehiscence is suspected)
- non-ferromagnetic stapedial implants
- pregnancy
- Claustrophobia that does not readily respond to oral medication
- Known allergy to gadolinium-based contrast agents.
- Renal failure as defined by a GFR less than 30 or the use of hemodialysis.
- Pregnant.
- Patients less than 13 years of age will be excluded.
- Interval treatment with radiation or surgery between the diagnostic MRI lesion identification and planned study MRI.
- Wards of the state

## 3.3 NUMBER OF PARTICIPANTS

One hundred (100) patients will be studied. Up to twenty (20) healthy volunteers will be studied for the purposes of MRI sequence optimization.

## 4 STUDY PLAN/DESIGN

### 4.1 Patient Enrollment:

Patients being evaluated for treatment of a suspected brain malignancy at MD Anderson Cancer Center will be screened for eligibility based on their screening diagnostic MRI scan and available clinical information. Once eligibility is confirmed, patients will be approached for protocol introduction and consenting and enrollment. Attempts will be made to scan patients in the 7T system within 30 days of an MRI scan performed at either 3T or 1.5T.

Up to twenty (20) healthy volunteers will be recruited through local advertisement for the purposes of MRI sequence optimization. Volunteers will be scanned in accordance with the UTMDACC Division of Diagnostic Imaging Policy # 3.00: Imaging of Healthy Volunteers for Quality Assurance/Improvement and Technical Development.

### 4.2 Procedure to Obtain Consent

The patients and volunteers will be approached in person or using IRB approved remote consent procedures by either the Diagnostic Imaging (DI) faculty or Research Staff, including research nurses and research coordinators for their approval before their procedure. For subjects' age 13-17 years old, a parental or LAR permission must be obtained and documented that the informed consent occurred prior to the study subject's entry into the study and prior to any study related procedures. During the consenting process, patients will be educated and consented for their

# Proprietary Information of MD Anderson

Protocol No: 2019-1032

Version No: 10

Version Date: August 25, 2023

research participation in this study. All subjects and volunteers who meet eligibility and complete the informed consent process will be registered in UTMDACC CORe system.

## 4.3 Houston Methodist Research Institute (HMRI) Registration

If inclusion/exclusion criteria are met and patients agree to participate in the study, the research study team will then contact the Houston Methodist Research Institute (HMRI) to register the patient and schedule their research MRI scan. Patient information including patient name, date of birth, prior allergic reaction to gadolinium based contrast agents, prior surgical history (as it pertains to surgical implants which may be a contraindication to MR scanning) which will be provided to HMRI as part of the study procedure (Appendix A – MRI Safety Questionnaire) and Referral Questionnaire for MDACC (Appendix B).

A copy of the completed MRI safety questionnaire and Referral Questionnaire for MDACC will be stored in REDCap and only authorized members of research team from MD Anderson (MDA) & HMRI who signed the delegation of authority log will have access to the data.

Research patients and volunteers will be contacted by MDA DI research study staff and given instruction for their research MRI scan once it is scheduled at HMRI.

## 4.4 MR Scanning:

Patients:

The study MRI will be performed on a 7.0-T MRI system. All patients will undergo conventional anatomic MR imaging including 3D T1 pre and post-contrast weighted imaging, 3D T2 weighted imaging, 3D T1 SPACE post-contrast, dynamic contrast-enhanced perfusion imaging, magnetic resonance spectroscopic imaging, functional magnetic resonance imaging (speech and motor paradigm), as well as the study-specific sequences to include:

- Quantitative MRI
- CEST
- Adv Diff
- Adv ASL

The entire scan time is expected to be approximately sixty (60) minutes. Routine and study sequences obtained on the 7T system may be obtained with the system in parallel transmit (pTx) scanning mode. Scanning in pTx mode can lead to increases in specific absorption rate (SAR) compared to single transmit mode; however, system software controls and sequences in both modes adheres to non-significant risk standards as defined by both IEC 60601 and the

# Proprietary Information of MD Anderson

Protocol No: 2019-1032

Version No: 10

Version Date: August 25, 2023

US Food & Drug Administration including specifically that the SAR for the head will be less than 3.2W/kg head.

Volunteers:

The study MRI will be performed on a 7.0-T MRI system. Volunteers will not get an IV line placed or receive contrast as per UTMDACC Division of Diagnostic Imaging Policy # 3.00: Imaging of Healthy Volunteers for Quality Assurance/Improvement and Technical Development.

Volunteers will undergo a selection of research sequences above for the purposes of sequence optimization and quality assurance. The volunteer scan time is expected to be approximately sixty (60) minutes. Routine and study sequences obtained on the 7T system may be obtained with the system in parallel transmit (pTx) scanning mode. Scanning in pTx mode can lead to increases in specific absorption rate (SAR) compared to single transmit mode; however, system software controls and sequences in both modes adheres to non-significant risk standards as defined by both IEC 60601 and the US Food & Drug Administration including specifically that the SAR for the head will be less than 3.2W/kg head.

## 4.5 Patient experience survey

Patients will be given a one-page survey regarding their experience in the 7T MRI system following their scan. For subjects' age 13-17 years old, Research study staff will review questionnaires for completeness and ask subjects with the presence of subject's parent or LAR to complete any missing responses.

4.5.1 [Appendix A]

## 4.6 Imaging Time Points

4.6.1 A single research imaging session will be planned for each patient. However, patients will still undergo follow-up imaging scans as part of their standard of care. These follow-up scans will serve as the basis for statistical analyses that consider treatment response or disease recurrence.

## 4.7 Conclusion of Study Participation:

4.7.1 Completion of planned study or volunteer scan.

4.7.2 Upon patient or volunteer request.

4.7.3 Death.

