## 7 STATISTICAL CONSIDERATIONS

### 7.1 Definitions

7.1.1 Lesion “**treatment response**” will be defined by size and contrast to noise ratio (CNR). Treatment response will be assessed only in patients with treatment prior to enrollment.

7.1.1.1 Size – treatment response in a single lesion will be considered as a decrease in size of 30%. (see section 5.1)

7.1.1.2 CNR—treatment response will be considered as a decrease in T1 post-contrast CNR of at least 20%. (see section 5.2) by standard T1 post-contrast imaging.

7.1.1.3 Lesions that do not meet these criteria for treatment response will be considered treatment failure.

7.1.2 Disease **recurrence** will be determined by surgical pathology (if available) or at least three months of imaging follow-up. Disease recurrence will be assessed only in patients with treatment prior to enrollment. Imaging findings will be considered recurrent disease in a lesion if:

7.1.2.1 The lesion was initially considered to be a treatment responder.

7.1.2.2 The lesion showed a successive increase in the size of 25% from nadir or a single imaging time point increase of 40%. (see section 5.1)

7.1.2.3 Lesions that do not meet these criteria will be considered radiation necrosis.

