## 7.4 Analysis Plan

Patients with metastasis are expected to have on average 2-3 detectable brain lesions each. Patients with primary brain tumors are expected to have a single lesion. All analyses will be performed on the largest lesion within patients, and some analyses will be repeated on a per-lesion basis.

The CNR for each imaging method will be determined and reported along with the corresponding 95% confidence interval. In secondary analyses, for the conspicuity endpoints, the T1 sequence by MRI will be considered the gold standard, and we will compare the conspicuity of each of the other methods to that of T1 sequencing by using McNemar's test. This analysis will first be performed in the largest lesion per patient, and then analyses will be repeated using all lesions.

If enough follow-up images are obtained (see section 4.5), we will compare the CNR in lesions that respond to treatment to those that do not by using a Wilcoxon rank-sum test. We will compare the CNR between baseline and follow-up within patient by using a Wilcoxon signed-rank test. Also, for those lesions that initially respond, some will subsequently grow in size after the initial response. Of these, some will be considered radiation necrosis and some progressive disease. The CNR will be compared between lesions with necrosis and those that are progressive disease using a Wilcoxon rank-sum test.

Exploratory aims will be analyzed with descriptive statistics. fMRI paradigms will be summarized by the group mean and standard deviation. Patient satisfaction will be reported on a five-point Likert scale and compared between the 7T scan and the most recent clinical scan by using a Wilcoxon rank-sum test.

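### Section 4.7.1 ends patient participation at the single 7T scan, but the response, recurrence and necrosis labels come from later routine data with no capture window, and under-followed lesions can default to necrosis

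*Combined protocol and SAP*

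**What the plan says.** Section 4.7 lists three events that conclude participation: "Completion of planned study or volunteer scan", a request by the participant, and death. It has no follow-up phase for patients.

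Section 4.6.1, immediately before it, states: "A single research imaging session will be planned for each patient". It adds that "patients will still undergo follow-up imaging scans as part of their standard of care", and then: "These follow-up scans will serve as the basis for statistical analyses that consider treatment response or disease recurrence".

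Section 7.1 supplies the labels:

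- **Treatment response (7.1.1):** a 30% fall in size and a fall of at least 20% in T1 post-contrast CNR are the criteria. No time point is attached.
- **Recurrence (7.1.2):** "Disease recurrence will be determined by surgical pathology (if available) or at least three months of imaging follow-up". On imaging, the lesion must first have responded, and must then show either a successive 25% increase from nadir or a 40% increase at one time point.
- **Radiation necrosis (7.1.2.3):** whatever does not meet the recurrence criteria.

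Section 7.4 opens the paragraph on follow-up analyses with a condition: "If enough follow-up images are obtained (see section 4.5), we will compare the CNR in lesions that respond to treatment". That paragraph holds the comparison of responders with non-responders, the baseline-to-follow-up comparison, and the rank-sum comparison of necrosis with progressive disease. Section 4.5, to which it points, is the patient experience survey. Imaging time points are in 4.6.

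**The concern.** The sole secondary objective (1.2.1) is about telling radiation necrosis from progressive disease. In 7.4 the only test that sets those two groups against each other is the rank-sum comparison of CNR, and it needs labels that cannot exist on the day of the scan unless pathology is already in hand. By then 4.7.1 has closed participation, and no other section says for how long, or for which patients, later records are to be collected.

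Three consequences follow:

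- **Unequal follow-up.** Lesions are labelled from whatever routine scans exist, so the chance of meeting a growth criterion rises with the length and number of scans.
- **A default that absorbs missing information.** As worded, 7.1.2.3 does not separate a lesion that was followed and stayed below the growth thresholds from one that was hardly followed.
- **A discretionary analysis.** With no definition of enough images, the decision to run the comparisons can be taken after the data are seen.

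Availability of later scans or pathology may also be related to outcome. That is plausible, but the documents contain nothing that shows it.

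**Working it through.** The point is mainly textual. The one relevant planning figure is the group size.

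**1. Plan's own figure.** Section 3.3 gives 100 patients. Section 7.3 assumes that 90% have metastasis or primary tumor, about half in each category, and about half of each treated. Expected size of each of the four groups: 100 × 0.90 / 4 = 22.5, within the stated 20 to 25.

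**2. Patients who can receive a label.** Response and recurrence are assessed only in patients treated before enrollment (7.1.1, 7.1.2). Expected number: 100 × 0.90 × 0.50 = 45.

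**3. Effect of incomplete capture.** The plan gives no share of treated patients with pathology or three months of imaging. Taking 100%, 75%, 50% and 25% as assumptions:

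| Share with adequate follow-up | Treated patients who can be labelled |
|---|---|
| 100% | 45 |
| 75% | 45 × 0.75 = 33.75, about 34 |
| 50% | 45 × 0.50 = 22.5, about 22 |
| 25% | 45 × 0.25 = 11.25, about 11 |

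These are upper limits for necrosis versus progression. Section 7.4 confines that comparison to lesions that first respond and later grow, and 7.1.2.1 also requires an initial response for recurrence on imaging. The plan gives no figure for that subset.

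**4. Sections side by side.**

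| Question | What the text gives |
|---|---|
| When does a patient's participation end? | At scan completion (4.7.1) |
| Where do the labels come from? | Later routine scans (4.6.1), or pathology for recurrence (7.1.2) |
| How long must follow-up be? | Three months or more for recurrence without pathology; nothing for response |
| When does capture stop? | Not stated |
| How much follow-up is enough? | Not stated; the pointer leads to the survey |
| What if follow-up is short or absent? | No rule, apart from the necrosis default in 7.1.2.3 |

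**5. How the default acts.** Take two lesions with the same course: both respond, begin to regrow, and eventually pass the 40% threshold. If routine imaging of the first continues past that point, it is recurrent. If imaging of the second stops earlier, it fails the criteria and is necrosis under 7.1.2.3. The label differs because the follow-up differs. The number of scans matters too: if a successive increase means more than one scan, a lesion with a single scan after nadir can qualify only through the 40% route.

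**6. Direction of the error.** Let Δ be the true difference in mean CNR between progression and necrosis, and m the share of the necrosis group that is really under-followed progression. If those lesions have the same CNR distribution as other progressive lesions, the expected observed difference is (1 − m) × Δ, an attenuation. If length of follow-up is itself related to CNR, the direction is not fixed. The documents give no value for m.

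**The case against.** The best defence is that 4.7 ends what the patient has to do, while 4.6.1 expressly keeps routine records in use. Other sections fit this reading: 6.1, 6.5 and 8 refer to policies on existing medical information, 6.1 collects record numbers and dates, and 6.4 shifts dates so that intervals within a patient are kept. No section says that capture stops at the scan. This stands as far as it goes. It supplies a data source, but no window, minimum or rule for lesions without follow-up.

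Section 7.4 also offers protection. If only lesions seen to respond and then grow enter the necrosis-versus-progression comparison, one with no follow-up at all should not reach it. That narrows the problem to lesions with short follow-up after growth begins. But 7.1.2.3 carries no such restriction, and the two sections are not aligned.

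A reader might infer more than the documents support:

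- **That the secondary objective has no on-study data.** The 7T measurements are on study and 4.6.1 designates the routine scans. What lacks a collection plan is the outcome label.
- **That every label needs three months of imaging.** That period is stated for recurrence only, with pathology as the alternative.
- **That all secondary analysis fails without labels.** The McNemar comparison with T1 uses none and can be run on the study scan. For the same reason it cannot by itself separate necrosis from progression.
- **That a withdrawal request after the scan has no effect.** No section says so. The consent pages were not available, so neither this nor consent to later record use can be judged.
- **That a power loss can be computed from 45 patients.** The planned test uses an unstated subset of them, and the capture rate and group split are not given.

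**Conclusion.** The concern holds as a failure to reconcile 4.7.1 with 4.6.1, 7.1.2 and 7.4. Outcome labels rest on routine data gathered after participation is declared over, with no cut-off, an undefined condition for analysis, a wrong cross-reference, and a default that can turn short follow-up into necrosis. The comparison serving objective 1.2.1 is therefore exposed to misclassification from unequal follow-up. The primary CNR estimates are not affected.

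At most about 45 treated patients are involved in the largest-lesion analysis, given the 90% and 50% assumptions in 7.3. The eligible number, the share with adequate follow-up and the misclassified share are all unknown, so no bias or power figure is claimed. The change should be made: it is more than a missing detail, because following the present text can produce wrong labels.

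**What to change.** 1. **Section 4.7.** End participation at scan completion for volunteers only. Keep patients on study, for data capture only, until the earliest of a fixed cut-off, death or withdrawal. The cut-off should cover at least the three months in 7.1.2; its exact length is the sponsor's choice.
2. **Section 4.6.** State that all routine brain MRI, pathology and therapy dates up to that cut-off are abstracted for every treated patient. Confirm that the consent covers this.
3. **Section 7.4.** Replace the condition about enough images with an analysis of all treated lesions classifiable at the cut-off, and correct the cross-reference from 4.5 to 4.6.
4. **Sections 7.1.2.3 and 7.4.** Report lesions without adequate follow-up as unclassified, with number and reasons, and not as necrosis. Make the two sections agree on which lesions enter the necrosis-versus-progression comparison.

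The cost is a protocol amendment, chart and PACS abstraction for about 45 patients, and a later database lock. No extra visit or scan is needed.
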